## Purpose of the Study

This project will use Self-system therapy (SST), an empirically validated intervention based to treat depression and lung-cancer-related distress in older adults (65 years and older). We hypothesize that psychological measures and physical performance measures as indicators of resilience will be acceptable and feasible to participants.

(Hypothesis 1) Participants will complete at least 80% of SST treatment sessions (Hypothesis 2). There will be an association between measures of psychological and physical resilience. (Hypothesis 3). Lastly, we hypothesize that participant's psychological and physical resilience scores will improve from baseline to post-intervention as a function of receiving the SST intervention.

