#### Subject Recruitment

Potentially eligible candidates will be identified from each oncology provider's clinic schedules via medical chart review. This pre-identification process involves pre-screening of patients using their medical records on major characteristics (e.g., disease stage, current treatment status,) to reduce the unnecessary burden of contacting patients who will not screen in or of contacting patients who may be ill. Study staff will contact providers to obtain approval (as needed) to contact the potential participant. If the provider approves, a letter from the patient's provider will be sent to a candidate summarizing the research study. We will include a phone number for the patient to call to indicate that she is not interested in pursuing the study further.

A total of 15 patients will be recruited from Duke Cancer Center to complete study procedures.

Participants will have the opportunity to consent electronically via redcap database or by paper over the telephone. After completing a baseline assessment, participants will be sent sealed study materials along with the instructions regarding the study interventionist's name and contact information. All sessions will be conducted by trained interventionists with a Masters or doctoral degree in psychology or clinical social work and certified competent in the interventions by the PI. [name] will hold regular supervision sessions among the interventionists to ensure adequate quality of the delivered interventions. All supervision sessions are confidential; no identifiable information about participants is retained in supervision records.

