#### Data Analysis & Statistical Considerations

Because this is a small pilot study with a small sample size power calculations are inappropriate. Below is a summary of the planned data analysis:

Descriptive statistics will be used to analyze SST-LC attendance, responses to questionnaire items, and sociodemographic data. Outcome measure data will be analyzed on an as per protocol basis. Standardized mean differences (with Hedges adjustment for small sample size) and 95% confidence intervals to examine the relative size of the intervention effect across the different measures. Scores are interpreted as positive intervention effects when the post-intervention values of negative affect are lower than baseline; and when post-intervention values of efficacy, affect, cognitive appraisal, coping, resilience, physical functioning and activity are higher than baseline. Psychological resilience and physical resilience self-report scores from baseline to 1-month follow-up will also be analyzed.

All quantitative analyses will be performed using IBM SPSS statistics software.

Participants enrolled in the study will complete participation across 2-4 months.

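### No score is named to decide the improvement hypothesis, and any favourable movement counts as an intervention effect, so the supporting measure can be chosen afterwards

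*Combined protocol and SAP*

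**What the plan says.** The last hypothesis under Purpose of the Study is that participants' "psychological and physical resilience scores will improve from baseline to post-intervention as a function of receiving the SST intervention". It fixes two constructs and one time point. It names no instrument or score, and neither does any other section.

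Data Analysis & Statistical Considerations plans "Standardized mean differences (with Hedges adjustment for small sample size) and 95% confidence intervals" in order "to examine the relative size of the intervention effect across the different measures". The reading rule begins "Scores are interpreted as positive intervention effects when" and has two parts:

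- "when the post-intervention values of negative affect are lower than baseline": one domain, lower is better.
- "post-intervention values of efficacy, affect, cognitive appraisal, coping, resilience, physical functioning and activity are higher than baseline": seven domains, higher is better.

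That makes eight domains. The rule refers only to direction. It sets no condition on the confidence interval, no minimum size of change and no order among the measures. The same section adds that "Psychological resilience and physical resilience self-report scores from baseline to 1-month follow-up will also be analyzed".

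Subject Recruitment gives the sample size: "A total of 15 patients will be recruited from Duke Cancer Center to complete study procedures". Design & Procedures describes a single arm without a control group.

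**The concern.** The hypothesis names constructs, and the text leaves open which scores stand for them. Background & Significance describes resilience through attributes such as coping, self-efficacy and positive emotions, and these overlap several of the eight analysis domains. Any of those domains could later be presented as psychological resilience. Physical resilience could be a performance measure (Purpose mentions these), a self-report score (the 1-month sentence), physical functioning, or activity.

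Two features of the plan combine here. The deciding score is open, and the reading rule is so permissive that some measure will almost always satisfy it. The hypothesis could then be reported as supported by whichever measure moved. A reader of the results could not tell a prespecified finding from the best of several. If the largest of the estimates were carried forward to a later trial, it would be biased upwards.

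**Working it through.** The plan states no power, alpha or error rate, so there is no figure of its own to reproduce. The check asks how often something favourable appears when nothing has changed.

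**Inputs from the documents**
- Post-intervention domains: 1 + 7 = 8, taken as one score each. Several instruments per domain would raise the figures below.
- 1-month comparisons: 2 (psychological and physical resilience self-report), giving 8 + 2 = 10 in all.
- Patients: n = 15.
- Intervals: 95%, so each leaves 2.5% on the favourable side when there is no change.

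**Assumptions not in the documents**
- Correlation between measures: a common value, tried from 0 to 0.9.
- Normally distributed changes, paired t intervals, 40,000 simulated trials per correlation.

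**Formula for k independent measures:** P(at least one) = 1 − (1 − p)^k, where p is the chance for one measure.

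**Step 1: the rule as written, direction only (p = 0.5)**
- k = 8: 1 − 0.5^8 = 0.996
- k = 10: 1 − 0.5^10 = 0.999

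**Step 2: a stricter rule, 95% interval wholly on the favourable side (p = 0.025)**
- k = 8: 1 − 0.975^8 = 0.183
- k = 10: 1 − 0.975^10 = 0.224

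**Step 3: allowing for correlation (simulated)**

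| Correlation | Direction only, 8 | Direction only, 10 | Interval rule, 8 | Interval rule, 10 |
|---|---|---|---|---|
| 0 | 0.996 | 0.999 | 0.186 | 0.225 |
| 0.5 | 0.887 | 0.907 | 0.130 | 0.149 |
| 0.8 | 0.748 | 0.767 | 0.084 | 0.093 |
| 0.9 | 0.682 | 0.699 | 0.062 | 0.068 |

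The row for zero correlation agrees with the formula to within simulation error.

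**Step 4: what naming scores achieves**
- One named score: 50% on direction only, 2.5% on the interval rule.
- Either of two named independent scores: 1 − 0.5^2 = 75% on direction only; 1 − 0.975^2 = 4.9% on the interval rule.
- Both of two named independent scores: 0.5^2 = 25% on direction only; 0.025^2 = 0.06% on the interval rule.

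Naming scores is therefore not enough while the direction-only wording stands. Whether either or both must improve also changes the meaning of a success.

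**Step 5: size of the largest estimate**
- Hedges factor for n = 15: 1 − 3/(4 × 14 − 1) = 0.9455.
- With no true change, and the effect taken as mean change divided by the SD of change, a single measure averages 0. The largest of 8 independent measures averages about 0.38 (simulated, 10,000 runs).
- Outcomes are to be analysed per protocol, so fewer than 15 patients may contribute. With 12 or 10 patients the average largest value is about 0.42 or 0.47.

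**The case against.** The strongest reply is that this is an estimation pilot. It plans no significance test of improvement and states no alpha or success threshold. One of its aims is to try out measures, so comparing effects across them is part of the purpose, and choosing two in advance may seem to prejudge what is to be learned. The direction sentence can also be read as a mere scoring convention that says which way is better on each scale. And Purpose already limits the hypothesis to psychological and physical resilience at post-intervention.

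Much of this stands. No error rate is breached and no alpha adjustment is called for. The constructs and the time point are set; what is missing is the scores. But the sentence as written does more than orient scales, because it says that favourable scores are interpreted as effects of the intervention. Naming two deciding scores does not stop the pilot from reporting and comparing every measure.

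Three stronger readings are tempting, and the documents do not support them:

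- A reader might infer that all eight domains are judged at two times, giving 16 comparisons and a chance of 1 − 0.975^16 = 33%. The 1-month sentence covers only the resilience self-report scores, so the text supports about 10.
- A reader might infer that the hypothesis is formally judged on all eight domains. No section says so. The difficulty is that the text does not say which scores count as resilience.
- A reader might infer that the effect found here will be used to size the larger trial. The aims at the end of Background & Significance mention a future larger RCT only in connection with prediction models, so the upward bias is conditional on such use.

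**Conclusion.** The concern holds as a problem of selective interpretation. The improvement hypothesis has no named deciding score, and the reading rule would declare a positive effect somewhere in most trials with no true change: about 99.6% for 8 independent measures, 89% at correlation 0.5 and 68% at 0.9. The correlations are assumed, but the chance exceeds two in three at every value tried.

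How likely a chance finding is depends on the rule. Requiring the 95% interval to lie wholly on the favourable side brings it down to about 18% for 8 measures and 22% for 10 if independent, or 13% and 15% at correlation 0.5. The benchmark for either of two named independent scores is about 5%.

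A favourable result being likely by chance is thus a consequence of the direction-only wording and would not follow under the interval rule. Pilot status excuses the absence of power and of multiplicity adjustment. It does not excuse a directional hypothesis whose deciding scores are left open.

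**What to change.** In Data Analysis & Statistical Considerations, before outcome data are examined:

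1. Name one psychological-resilience score and one physical-resilience score, each as change from baseline to post-intervention, as the results on which the improvement hypothesis is judged. State whether both must improve or either is enough.
2. Replace the direction-only sentence with interpretation by the estimate and its 95% confidence interval. Keep the direction only as a scoring convention.
3. State that all other measures and the 1-month resilience scores will be reported in full as descriptive results and not called intervention effects.

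No multiplicity correction is needed. The change takes a few sentences and needs no extra patients, visits or data. The small downside is less freedom to highlight other measures.

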#### Design & Procedures

Fifteen older adults (ages 65 and older) will be recruited from clinics of the Duke Cancer Institute.

Older adults with lung cancer will receive the SST intervention with sessions that range between 8 (recommended minimum number of sessions) to a maximum of 12 sessions lasting on average of 30-45 minutes. The intervention will be delivered by video conference. The design is a single-arm study, with no control or placebo group condition.

The four content/topic areas that are covered across the 8-12 SST intervention sessions are as follows:

1) Orientation Phase of SST. Participants are provided with a rationale for treatment that focuses on the importance of self-regulation for well-being in the context of advanced cancer.

2) Exploration Phase of SST. This phase consists of having patients examine successful and unsuccessful interpersonal interactions, functional difficulties, and their self-evaluations and goal pursuit strategies while coping with advanced cancer. Patients then identify and analyze their explicit or implicit preferences for certain kinds of personal goals.

3) Adaptation Phase of SST. The patient and interventionist work together to address each treatment goal, using change strategies and compensatory strategies that include helping the patient to modify goals or to learn to pursue them via different means that are a better fit to their current life circumstances, physical, limitations, or personality traits.

4) A maintenance plan is developed with each patient. The maintenance plan includes a list of strategies to be used daily (e.g. self-monitoring forms), short-term goals (e.g. becoming more active in self-rewarding activities) and long-term goals.

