#### **Importance of the Knowledge to be Gained:**

The risks associated with this study are small compared to the information that will be obtained. The information gathered may lead to major advances in our understanding of how to protect the emotional

health physical health of patients with lung cancer. If successful, it may enlarge our repertoire of methods for effectively enhancing the well-being of cancer patients.

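### Before-after change in a single-arm study is labelled an intervention effect, with no caveat that the design cannot attribute it to SST

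*Combined protocol and SAP*

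**What the plan says.** Data Analysis & Statistical Considerations plans Hedges-adjusted standardised mean differences with "95% confidence intervals to examine the relative size of the intervention effect across the different measures". The next sentence reads "Scores are interpreted as positive intervention effects when the post-intervention values of negative affect are lower than baseline", and goes on to list seven further domains for which a higher post-intervention value counts as favourable. Baseline to 1-month follow-up scores will also be analysed.

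The last hypothesis in Purpose of the Study is that "participant's psychological and physical resilience scores will improve from baseline to post-intervention as a function of receiving the SST intervention".

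Design & Procedures states: "The design is a single-arm study, with no control or placebo group condition". Subject Recruitment sets the size: "A total of 15 patients will be recruited from Duke Cancer Center to complete study procedures". On duration, the analysis section says: "Participants enrolled in the study will complete participation across 2-4 months".

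No section says that uncontrolled change cannot be attributed to SST.

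**The concern.** *Intervention effect* and the causal phrase in the hypothesis both say that SST produced the change. In a one-group study the observed change is the sum of any SST effect and everything else that moved the scores over the same period. Several such influences are plausible here:

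- **Disease course.** The inclusion criteria require stage III-IV lung cancer, and participation lasts 2-4 months.
- **Cancer treatment.** The entry criteria neither require nor exclude active treatment. Subject Recruitment mentions "disease stage, current treatment status" only as examples of pre-screening characteristics.
- **Retesting.** The same measures are repeated after baseline.
- **Chance.** The planned sample is 15.

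Regression to the mean is possible but less likely, because no entry criterion uses a score.

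These influences need not favour SST. Decline in physical functioning, for example, could hide a real benefit. What is at stake is the conclusion of the report: followed as written, the plan credits a favourable change to SST, and it gives no way to recognise an effect masked by decline.

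**Working it through.** The plan has no power or sample-size figure to reproduce; it says that power calculations are inappropriate at this size. The check asks whether the planned 95% CIs protect against misattribution.

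**Inputs**
- From the documents: n = 15 (Subject Recruitment), 95% CIs (analysis section), one arm (Design & Procedures).
- Assumed: change scores are normal, the true SST effect is zero, and the mean drift from other causes is δ, in SDs of the change score. The documents give neither a size nor a direction for δ, so the values below are illustrative.

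**Step 1: when the CI lies above zero.** The paired-change 95% CI lies above zero when the observed standardised change exceeds t(0.975, n-1)/√n. With n = 15, t(0.975, 14) = 2.145 and the threshold is 2.145/√15 = 0.554 SD of change. The Hedges factor is J = 1 - 3/(4×14 - 1) = 0.945. It rescales the estimate but does not change its sign.

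**Step 2: how often drift alone does this.** The t statistic follows a noncentral t distribution with 14 degrees of freedom and noncentrality δ√15. The chance required is P(T > 2.145).

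| Assumed drift δ | δ√15 | P(95% CI above zero), no SST effect |
|---|---|---|
| -0.2 | -0.775 | 0.4% |
| 0 | 0 | 2.5% |
| +0.2 | 0.775 | 10.8% |
| +0.3 | 1.162 | 19.0% |
| +0.5 | 1.936 | 43.8% |

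**Step 3: fewer analysed patients.** Outcomes are to be analysed per protocol, so fewer than 15 may contribute. No dropout rate is given. If 12 or 10 were analysed (assumed), the CI half-width would grow from 0.55 to 0.64 or 0.72 SD of change. At δ = +0.5 the chance in Step 2 would be 35% or 29%. The CI then excludes zero less often, but it still describes total change and not the part due to SST.

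**Reading.** With no drift the CI behaves as intended: 2.5% on the favourable side. With favourable drift it reports a real before-after change that SST did not cause. With unfavourable drift it almost never lies above zero, and a true SST effect of similar size would be offset. The interval measures sampling error in the change. It cannot say what caused it.

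**The case against.** The strongest reply is that the study is modest and open about its limits. The analysis section calls it a small pilot and Design & Procedures states the single arm. The end of Background & Significance limits the aims to testing measures and their association ahead of a larger RCT. A causal hypothesis may motivate a pilot that cannot confirm it, and harm arises only if the report overclaims. That keeps the point small. It does not remove it, because the analysis section itself prescribes the causal label.

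Three stronger readings are tempting, and the documents do not support them.

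- A reader might infer that direction alone decides whether SST worked. Read that way, a measure with no true change would be called positive half the time. At least one of the eight listed domains would be positive with probability 1 - 0.5^8 = 99.6% if independent, or about 75% at an assumed correlation of 0.8. But the sentence directly follows the plan for estimates with 95% CIs, and it sorts measures into those that improve by falling and those that improve by rising. It is most naturally a sign convention, and no decision is tied to it. What stands is that it is worded as an interpretation criterion and should be clarified.
- A reader might infer that the plan foresees an effectiveness claim, from "If successful, it may enlarge our repertoire of methods for effectively enhancing the well-being of cancer patients". That is conditional language in a statement of potential value, not a reporting rule.
- A reader might infer that the bias must favour SST. The documents give no direction, and unfavourable drift is at least as conceivable for physical functioning and activity.

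**Conclusion.** The attribution point holds and is minor. The stated label, applied exactly, gives a conclusion that a study without a control group cannot support, and nothing in the documents qualifies it. The CIs do not repair this: with no SST effect and n = 15, they lie above zero between 0.4% and 44% of the time across the drift values tried (-0.2 to +0.5 SD of change). Those values, and normality of the change scores, are assumptions. The conclusion does not depend on them, because it follows from the absence of a comparator. The direction sentence is a secondary matter of clarity. The design, data, study procedures and progression decisions are unaffected.

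**What to change.** Three wording changes:

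1. In Data Analysis & Statistical Considerations, replace *intervention effect(s)* with *change from baseline to post-intervention*, and describe the 1-month follow-up comparison as change from baseline.
2. In Purpose of the Study, reword the last hypothesis to: *among participants receiving SST, psychological and physical resilience scores will improve from baseline to post-intervention*.
3. In the analysis section, state that the listed directions only define which sign is favourable, and that each result is interpreted from its Hedges-adjusted estimate and 95% CI. No cut-off rule for CIs that include zero is proposed.

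These use estimates and intervals already planned and need no new data, patients, procedures or analyses. The cost is a less favourable conclusion: the report can describe change during SST but cannot claim an effect of SST.
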